# 9.0 ADVERSE EVENT DATA COLLECTION AND MONITORING

#### 9.1 **Definitions**

- 9.1.1 Adverse event (AE) Any unfavorable and unintended sign (including an abnormal laboratory finding), symptom, or disease temporally associated with the use of a medical treatment or procedure regardless of whether it is considered related to the medical treatment or procedure (attribution of unrelated, unlikely, possible, probable, or definite). Medical conditions or diseases present before starting the investigational drug will be considered as treatment-related AEs if they worsen after starting study treatment.
- 9.1.2 Unexpected AE Any adverse event not listed in Tables 3-6.
- 9.1.3 **Serious AE –** Any adverse drug experience occurring at any dose that results in any of the following outcomes:
  - death;
  - a life-threatening adverse drug experience;
  - inpatient hospitalization, or prolongation of existing hospitalization (as defined below in this section);
  - a persistent or significant disability/incapacity; or a congenital anomaly/birth defect.
  - Important medical events that may not result in death, be life threatening, or require hospitalization may be considered a serious adverse drug experience when, based upon medical judgment, they may jeopardize the patient or participant and may require medical or surgical intervention to prevent one of the outcomes listed in this definition.
  - Hospitalization for expedited AE reporting purposes is defined as an inpatient hospital stay equal to or greater than 24 hours. Hospitalization is used as an indicator of the seriousness of the adverse event and should be reserved for situations where the adverse event truly fits this definition and not for hospitalizations associated with less serious events. For example, the following are not considered serious adverse events:
    - a hospital visit where a patient is admitted for observation or minor treatment (e.g. hydration) and released in less than 24 hours

- hospitalization for pharmacokinetic sampling
- o admission to hospice
- hospitalizations planned before entry into the clinical study
- hospitalization for elective treatments
- hospitalizations to work up Grade 1 adverse events
- 9.1.4 **Unanticipated problem -** An unanticipated problem is any event/experience that meets ALL 3 criteria below:
  - Is unexpected in terms of nature, severity or frequency given the research procedures that are described in the protocolrelated documents AND in the characteristics of the participant population being studied.
  - Is related or possibly related to participation in research. This means that there is a reasonable possibility that the incident may have been caused by the procedures involved in the research study.
  - The incident suggests that the research placed the participant or others at greater risk of harm than was previously known or recognized OR results in actual harm to the participant or others.
- 9.1.5 **Protocol Violation-** A protocol violation is defined as any change, deviation, or departure from the study design or procedures of a research project that is NOT approved by the institution's IRB prior to its initiation or implementation, OR deviation from standard operating procedures, Good Clinical Practices (GCPs), federal, state or local regulations. Protocol violations may or may not be under the control of the study team or UVa staff. These protocol violations may be major or minor violations.
- 9.1.6 **Suspected Adverse Reaction (as defined in 21 CFR 312.32 (a))-** Any adverse event for which there is a reasonable possibility that the drug caused the adverse event.

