#### 8.2 Evaluation of Sample Populations and Criteria

8.2.1 Safety

All participants receiving any protocol treatment will be evaluated for safety.

The 6MHP vaccine has been safe, with lower toxicities than with class I peptides, in particular with lower autoimmune or hyperimmune toxicities. Ipilimumab causes toxicities related to unmasking autoimmunity, some of which can be severe, but are managed well with steroids. We do not

anticipate increased autoimmune toxicities by combining 6MHP vaccine with ipilimumab, but relatively high rates of hypophysitis have been reported by combining ipilimumab with each of two other vaccines. Thus, this trial will be designed with stopping rules for toxicities beyond those expected with ipilimumab alone. Formal safety bounds (Section 8.5) based upon monitoring dose limiting toxicities (DLT) will guide decisions about early stopping due to potential safety concerns. If a stopping bound is crossed then accrual to the study will be suspended until the study PI, co-investigators and the DSMC can review the data, and determine if the study should continue, be amended or be closed to further accrual. The proposed safety bound will be applied overall and within cohort.

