# 9.2 Attribution Assessment

9.2.1 Attribution – The determination of whether an adverse event is related to a medical treatment or procedure. The attribution groups are:

Definite – Applies to those adverse events which, the investigator feels are incontrovertibly related to study drug. An adverse event may be assigned an attribution of definitely related if or when (must have all of the following):

- It follows a reasonable temporal sequence from administration of the test drug.
- It could not be reasonably explained by the known characteristics of the participant's clinical state, environmental or toxic factors, or other modes of therapy administered to the participant.
- It disappears or decreases on cessation or reduction in dose

with re-exposure to drug. (Note: This is not to be constructed as requiring re-exposure of the participant; however, the group of definitely related can only be used when a recurrence is observed.)

• It follows a known pattern of response to the test drug.

Probable – Applies to those adverse events for which, after careful consideration at the time they are evaluated, are felt with a high degree of certainty to be related to the test drug. An adverse event may be considered probably related if or when (must have three of the following):

- It follows a reasonable temporal sequence from administration of the test drug.
- It could not be reasonably explained by the known characteristics of the participant's clinical state, environmental or toxic factors, or other modes of therapy administered to the participant.
- It disappears or decreases on cessation or reduction in dose. There are important exceptions when an adverse event does not disappear upon discontinuation of the drug, yet drugrelatedness clearly exists (e.g. bone marrow depression, fixed drug eruptions, tardive dyskinesia).
- It follows a known pattern of response to the test drug.

Possible – Applies to those adverse events for which, after careful consideration at the time they are evaluated, a connection with the test drug administration appears unlikely but cannot be ruled out with certainty. An adverse event may be considered possibly related if or when (must have two of the following):

- It follows a reasonable temporal sequence from administration of the test drug.
- It could not readily have been produced by the participant's clinical state, environmental or toxic factors, or other modes of therapy administered to the participant.

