- It follows a known pattern of response to the test drug.

Unlikely – Applies to those adverse events for which, after careful consideration at the time they are evaluated, are judged to be unrelated to the test drug. An adverse event may be considered unlikely if or when (must have two of the following):

- It does not follow a reasonable temporal sequence from administration of the test drug.
- It could readily have been produced by the participant's clinical state, environmental or toxic factors, or other modes of therapy administered to the participant.
- It does not follow a known pattern of response to the test drug.
- It does not reappear or worsen when the drug is readministered.

Unrelated – Applies to those adverse events, which after careful consideration, are clearly and incontrovertibly due to extraneous causes (disease, environment, etc.).

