# 9.9 **Dose-limiting Toxicities (DLT)**

#### 6MHP

A DLT of the 6MHP vaccine is defined as any unexpected Grade 3 or greater hematologic or non-hematologic toxicity that is definitely, probably, or possibly related to the administration of the vaccine. Small ulcerations of the skin at vaccine sites are expected. Thus, ulcerations will be considered DLTs only if the ulcers are  $\geq 2$  cm in diameter, require antibiotics or surgical debridement.

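### Section 9.1.1 deems any worsening of a pre-existing condition treatment-related, which conflicts with the event-by-event attribution in 9.2.1 and leaves the related-AE and DLT counts open to two readings

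*Combined protocol and SAP*

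**What the plan says.** **Section 9.1.1, AE definition.** An AE is any unfavorable sign, symptom or disease that follows treatment in time, "regardless of whether it is considered related to the medical treatment or procedure (attribution of unrelated, unlikely, possible, probable, or definite"). The next and last sentence of the same item says: "Medical conditions or diseases present before starting the investigational drug will be considered as treatment-related AEs if they worsen after starting study treatment". It is mandatory, has no exception, and names neither an attribution category nor an agent.

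**Section 9.2.1, attribution.** Attribution is "The determination of whether an adverse event is related to a medical treatment or procedure", on five levels. Unrelated is for events that "are clearly and incontrovertibly due to extraneous causes (disease, environment, etc".). One criterion for Unlikely, of which two must be met, is: "It could readily have been produced by the participant's clinical state, environmental or toxic factors, or other modes of therapy administered to the participant".

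**Section 9.9, DLTs.** A vaccine DLT is "any unexpected Grade 3 or greater hematologic or non-hematologic toxicity that is definitely, probably, or possibly related to the administration of the vaccine". An ipilimumab DLT must be related on the same three levels and must require permanent discontinuation of ipilimumab. A DLT that cannot be assigned to either agent is assigned to both. Section 9.1.2 calls an AE unexpected if it is not in Tables 3-6.

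**Sections 8.2.1, 8.5 and 8.6, monitoring.** Participants with a DLT are counted against Table 8. "The proposed safety bound will be applied overall and within cohort". Crossing suspends accrual until the investigators and the DSMC have reviewed the data. Section 8.6 calls the bounds non-binding.

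**Section 9.4.2, recording.** All AEs are reported through 30 days after the last dose, whatever the attribution. After that, only AEs possibly, probably or definitely related are recorded, until treatment follow-up ends.

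**The concern.** Melanoma is present at entry in cohorts 1 and 2, and participants in any cohort may have comorbidity that eligibility allows, such as mild arthritis or diabetes with HgB-A1C up to 7.5%. If such a condition worsens for reasons unconnected with study drug, 9.1.1 makes the event treatment-related and 9.2.1 makes it Unrelated or Unlikely. Two people coding the same event can each follow the protocol and record opposite answers.

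Relatedness decides several things in this trial: the related/unrelated split in the safety summary, which AEs are recorded after the 30-day window, the OnCore timelines in Table 10 and, for some events, whether a participant counts as a DLT. Safety is a primary objective and Table 8 is its formal monitoring rule. If disease-driven events are counted as DLTs, the rule can halt accrual for reasons other than drug toxicity.

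**Working it through.** **1. The two rules side by side.** Take a worsening of a baseline condition that is clearly due to that condition.

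- Under the last sentence of 9.1.1 it is treatment-related.
- Under 9.2.1 it is Unrelated.
- No section states an order of precedence. Section 6.6 lists progression as a reason to discontinue separately from DLT, and 8.2.3 captures it through PFS and DFS. Neither says that progression is not an AE or a DLT.

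**2. What depends on the label.**

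- AEs captured through 30 days after the last dose: unchanged (9.4.2).
- AEs recorded later, until treatment follow-up ends (24 months or start of another therapy, 6.1): affected, because only related AEs are kept.
- Timelines: affected. In Table 10, an unexpected Grade 2 event has 30 days if unrelated or unlikely, and 15 days if possible or higher.
- DLT count: affected only if the event is also unexpected and Grade 3 or greater (vaccine), or requires permanent discontinuation of ipilimumab.

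**3. Reproducing the plan's bound.** Inputs from Section 8.5: p0 = 0.15, p1 = 0.30, both nominal errors 0.10.

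- Odds ratio = (0.30 × 0.85)/(0.15 × 0.70) = 0.255/0.105 = 2.429, and ln(2.429) = 0.887.
- Slope = ln(0.85/0.70)/0.887 = 0.2188. The plan gives 0.219.
- Upper intercept = ln(0.90/0.10)/0.887 = 2.476. The plan gives 2.476.
- Rounding slope × n + intercept up to the next integer gives Table 8 at every n from 4 to 27 except n = 16, where the line is 5.98 (bound 6) and the table prints 7. That is a separate and small matter: at a 15% DLT rate, crossing by n = 27 is 4.5% with the table and 4.8% with the line.

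**4. Sensitivity of Table 8 to miscounted events.** The documents give no rate of worsening pre-existing conditions, so the share m is an assumption. Let the true DLT rate be 15%, and let an independent share m of participants have a worsened condition that meets the other DLT criteria and is counted. Table 8 counts participants, so the effective rate is p = 1 − 0.85 × (1 − m).

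Exact recursion, with q(n, x) the probability of x participants with a DLT among n without an earlier crossing: q(n, x) = (1 − p) q(n−1, x) + p q(n−1, x−1). From n = 4, probability at or above the printed bound is removed and summed, with a check after every participant.

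| m (assumed) | p | Crossing by n = 27 |
|---|---|---|
| 0 | 0.150 | 4.5% |
| 2% | 0.167 | 7.3% |
| 5% | 0.1925 | 13.2% |
| 10% | 0.235 | 27.6% |

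For scale, a true DLT rate of 30% with no miscounting crosses with probability 55.4%. If 9.2.1 governs in practice, m is near 0 and the first row applies.

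**The case against.** The best reply is that 9.9 leads back to 9.2. The DLT definitions use the words definitely, probably and possibly, and only 9.2.1 defines them. Because 9.1.1 assigns no category and no agent, a coder working through 9.9 would have to use 9.2.1, and an event clearly due to disease would drop out. This is a reasonable reading and may be the intended one. It is not stated, and the 9.1.1 sentence is worded as a rule.

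The rest of the reply limits the size of the problem, and it stands:

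- Table 3 lists tumor pain, abdominal pain, fatigue, dyspnea, low hemoglobin, AST, ALT and bilirubin. Under 9.1.2 these are expected and cannot be vaccine DLTs. (The by-grade rule in 1.5 and 1.6 is narrower and would leave more of them unexpected.)
- Cohort 3, expected to be the largest, enters with no evidence of disease, so a recurrence is arguably not a condition present before treatment. Comorbidity remains.
- Eligibility limits comorbidity: ECOG 0 or 1, no NYHA class III or IV, no HgB-A1C above 7.5%.
- Crossing leads to review, and the bounds are non-binding.
- Presuming that worsening of an allowed immune condition is related could be a deliberate cautious choice with ipilimumab. The plan does not say so, and its sentence covers every condition.

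A reader might also infer more than the documents support:

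- That every worsening automatically becomes a DLT. Grade, expectedness or permanent discontinuation, and attribution still apply.
- That the sentence changes what enters the primary safety endpoint. Within the 30-day window it does not, because AEs are reported regardless of attribution.
- That the roughly 70% without disease control in Table 2 (64/91) approximates the miscounting rate in cohort 1. That figure is lack of RECIST disease control on vaccine without ipilimumab, not a rate of unexpected Grade 3 events. Also, 27 participants at about 16 per year take about 1.7 years; at 1-3 per year that gives cohort 1 about 2 to 5 participants, while Table 8 starts at 4.
- That 5 or 10 points can be added to the 15% rate, giving 15% or 34% for crossing. This counts a participant with both kinds of event twice.
- That a comparison with the prior rates in Table 3 is spoiled. Sections 8.5 and 8.6 plan no such comparison, and the documents do not say how the earlier trials handled pre-existing conditions.

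**Conclusion.** The conflict is real: for a worsening caused by disease or comorbidity, 9.1.1 and 9.2.1 give opposite labels, and the documents do not say which prevails or how progression is to be counted. Read literally, 9.1.1 mislabels such events as related. That affects the related/unrelated split, recording after the 30-day window and reporting timelines with certainty, and the DLT count only through events that meet every other criterion in 9.9.

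The effect on Table 8 cannot be estimated from the documents. The rise from 4.5% to 7%, 13% or 28% rests on an assumed 2%, 5% or 10% miscounted share, independence from true DLTs, a true rate of 15%, and a check after each participant. It shows that the bound is sensitive to a few miscounted participants, not that miscounting at that level is expected. The point should be corrected because the text states a rule that contradicts another, the correction is cheap, and safety is a primary objective.

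**What to change.** Reconcile 9.1.1 with 9.2.1 and 9.9 in two sentences.

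1. In 9.1.1, replace the clause that deems worsened conditions treatment-related with: *will be recorded as AEs if they worsen, with attribution assigned under Section 9.2*.
2. Add that melanoma progression is captured as an outcome under 8.2.3 and counts toward DLTs only if the event is attributed to a study drug under 9.2.

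Worsening that the investigator attributes to vaccine or ipilimumab stays countable. The change needs no new visits or data, since Table 10 already requires an attribution for AEs, and it alters neither Table 8 nor any treatment rule. The cost is a short amendment with the IRB review that 10.1 requires. If any worsened pre-existing condition has already been coded under 9.1.1, its attribution should be checked against 9.2.1 when the amendment takes effect.

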# 9.2 Attribution Assessment

9.2.1 Attribution – The determination of whether an adverse event is related to a medical treatment or procedure. The attribution groups are:

Definite – Applies to those adverse events which, the investigator feels are incontrovertibly related to study drug. An adverse event may be assigned an attribution of definitely related if or when (must have all of the following):

- It follows a reasonable temporal sequence from administration of the test drug.
- It could not be reasonably explained by the known characteristics of the participant's clinical state, environmental or toxic factors, or other modes of therapy administered to the participant.
- It disappears or decreases on cessation or reduction in dose

with re-exposure to drug. (Note: This is not to be constructed as requiring re-exposure of the participant; however, the group of definitely related can only be used when a recurrence is observed.)

• It follows a known pattern of response to the test drug.

Probable – Applies to those adverse events for which, after careful consideration at the time they are evaluated, are felt with a high degree of certainty to be related to the test drug. An adverse event may be considered probably related if or when (must have three of the following):

- It follows a reasonable temporal sequence from administration of the test drug.
- It could not be reasonably explained by the known characteristics of the participant's clinical state, environmental or toxic factors, or other modes of therapy administered to the participant.
- It disappears or decreases on cessation or reduction in dose. There are important exceptions when an adverse event does not disappear upon discontinuation of the drug, yet drugrelatedness clearly exists (e.g. bone marrow depression, fixed drug eruptions, tardive dyskinesia).
- It follows a known pattern of response to the test drug.

Possible – Applies to those adverse events for which, after careful consideration at the time they are evaluated, a connection with the test drug administration appears unlikely but cannot be ruled out with certainty. An adverse event may be considered possibly related if or when (must have two of the following):

- It follows a reasonable temporal sequence from administration of the test drug.
- It could not readily have been produced by the participant's clinical state, environmental or toxic factors, or other modes of therapy administered to the participant.
- It follows a known pattern of response to the test drug.

Unlikely – Applies to those adverse events for which, after careful consideration at the time they are evaluated, are judged to be unrelated to the test drug. An adverse event may be considered unlikely if or when (must have two of the following):

- It does not follow a reasonable temporal sequence from administration of the test drug.
- It could readily have been produced by the participant's clinical state, environmental or toxic factors, or other modes of therapy administered to the participant.
- It does not follow a known pattern of response to the test drug.
- It does not reappear or worsen when the drug is readministered.

Unrelated – Applies to those adverse events, which after careful consideration, are clearly and incontrovertibly due to extraneous causes (disease, environment, etc.).

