# 8.5 Safety Monitoring

Toxicities will be monitored using CTCAE 4.03 criteria, with a focus on recording immune-related adverse events (irAE) (9). Stopping rules will be based on an expected irAE rate of 15-20%, where 10-15% had grade 3-4 irAE in one study (38) and in another 19% had grade 3, and 3.2% grade 4 irAEs (59). Significant increases over these rates are not expected but would be a reason for early discontinuation. Thus, formal safety bounds based upon the observed number of participants who experience a DLT as defined in Section 9.9 will guide decisions about early stopping due to potential safety concerns (Table 8). The definition of

DLT considers both irAEs and previously reported DLTs related to vaccine. If a stopping bound is crossed then accrual to the study will be suspended until the study PI, co-investigators and the DSMC can review the data, and determine if the study should continue, be amended or be closed to further accrual. The rate of DLTs will be monitored up to 30 days after the last vaccination. A sequential probability ratio test (SPRT) based upon a binomial test of proportions for DLTs will be used. Only the upper boundary will be used for monitoring to protect against excessive failure rates. The stopping boundary are for a SPRT contrasting a 15% versus 30% DLT rate, with nominal type I and II errors of 10% and 10%, respectively. The slope of the parallel lines for monitoring is 0.219 and the intercept for the upper bound is 2.476.

•	ie o. Otopping Oulde	
	Number of participants	Boundary
	4-6	≥4
	7-11	≥ 5
	12-15	≥6
	16-20	≥7
	21-25	≥ 8
	26-27	≥ 9

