# Table 10: AE reporting

\*Enter into OnCore database within 24 hours if unexpected and definitely related to protocol specified treatment

Hospitalization defined as an inpatient hospital stay or prolongation of a hospital stay equal to or greater than 24 hours

a Grade 1 unexpected or expected hematologic/metabolic events will be recorded in the Cancer Center Database; however, regardless of attribution, these events do not have to be reported.

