# 9.6.2 IRB Reporting Requirements

The University of Virginia is responsible for reporting to the UVA IRB-HSR per the following guidelines (Table 11):

Table 11:	ινα	IRB-HSR	reporting
	017		reporting

Type of Event	To whom will it	Time Frame for	How reported?
	be reported:	Reporting	
Any internal event resulting in death that is deemed DEFINITELY related to (caused by) study participation (Note: An internal event is one that occurs in a subject enrolled in a UVa protocol.)	IRB-HSR	Within 24 hours	IRB Online and phone call www.irb.virginia.edu/
Internal, Serious, Unexpected adverse event.	IRB-HSR	Within 7 calendar days from the time the study team received knowledge of the event. Timeline includes submission of signed hardcopy of AE form .	IRB Online www.irb.virginia.edu/
Unanticipated Problems that are not adverse events or protocol violations This would include a Data Breach.	IRB-HSR	Within 7 calendar days from the time the study team received knowledge of the event.	Unanticipated Problem report form. http://www.virginia.edu/vprgs/irb/ HSR_docs/Forms/Reporting_Re guirements- Unanticipated_Problems.doc )
Protocol Violations ( The IRB-HSR only requires that MAJOR violation be reported, unless otherwise required by your sponsor, if applicable. ) Or Enrollment Exceptions	IRB-HSR	Within 7 calendar days from the time the study team received knowledge of the event.	Protocol Violation and Enrollment Exception Reporting Form http://www.virginia.edu/vprgs/irb/ hsr_forms.html

Data Breach	The UVa Corporate Compliance and Privacy Office and	As soon as possible and no later than 24 hours from the time the incident is identified.	UVa Corporate Compliance and Privacy Office- [contact]
	ITC: if breach involves electronic data-	As soon as possible and no later than 24 hours from the time the incident is identified.	ITC: Information Security Incident Reporting procedure, http://www.itc.virginia.edu/securit y/reporting.html
	UVa Police if breach includes such things as stolen computers.	IMMEDIATELY.	Phone- [contact]

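### Under Section 9.2.1 a drug-related death from a first-occurrence event cannot be classed 'definite', so it misses both 24-hour reporting routes

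*Combined protocol and SAP*

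**What the plan says.** **Attribution (Section 9.2.1).** 'Definite' needs all of its listed criteria. One is "It disappears or decreases on cessation or reduction in dose". The words that follow, about re-exposure, are broken in the available text, but the note attached to them is intact. It says "This is not to be constructed as requiring re-exposure of the participant" and then that "the group of definitely related can only be used when a recurrence is observed". 'Probable' needs only three of four criteria, and its resolution criterion carries an explicit exception for drug-related events that do not disappear. 'Definite' has no such exception.

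**24-hour routes.** Table 11 (Section 9.6.2) requires IRB notice within 24 hours for "Any internal event resulting in death that is deemed DEFINITELY related to (caused by) study participation". The Table 10 footnote reads "Enter into OnCore database within 24 hours if unexpected and definitely related to protocol specified treatment".

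**Slower routes.**
- Section 9.6.1: DLTs enter OnCore within 5 calendar days.
- Table 11, next row: 7 calendar days to the IRB for an event described as "Internal, Serious, Unexpected adverse event".
- Section 9.6.3: 7 calendar days to the FDA for unexpected fatal or life-threatening suspected reactions.

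**Expectedness.** Section 9.1.2 defines an unexpected event as "Any adverse event not listed in Tables 3-6", with no mention of grade. Sections 1.5 and 1.6 define expectedness grade by grade, with a 4% threshold.

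**Accrual.** Section 8.5 says that "formal safety bounds based upon the observed number of participants who experience a DLT as defined in Section 9.9 will guide decisions" about early stopping. Section 8.6 calls these bounds non-binding.

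**The concern.** The fastest escalation in the protocol is reserved for an attribution category whose entry conditions the worst outcome will usually fail. A fatal event does not resolve, and one that kills at its first appearance cannot be seen to recur. Section 6.6 also calls for stopping the agent to which a DLT is attributed, so recurrence will seldom be observable for the most serious toxicities.

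What is at stake is how soon the IRB hears of a treatment-related death. The protocol treats such deaths as foreseeable. Section 1.6 cites five immune-related deaths in an adjuvant ipilimumab trial, though at 10 mg/kg rather than this trial's 3 mg/kg. Section 8.2.1 notes relatively high hypophysitis rates when ipilimumab was combined with two other vaccines. Cohort 3, expected to accrue fastest, consists of patients free of disease after resection.

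**Working it through.** **Step 1. Can a first-occurrence fatal event be 'definite'?** Taking the Section 9.2.1 conditions in turn:
- Reasonable timing after dosing: can be met.
- No other reasonable explanation: can be met.
- Resolves or lessens: not met by a death.
- Recurrence observed: not met, because there was one occurrence.
- Known pattern of response: can be met.

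All are required, so 'definite' fails. 'Probable' needs three of four, and timing, no other explanation and known pattern supply three. The highest reachable class is 'probable'.

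**Step 2. Which routes remain for that death?**

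| Route | Trigger | Deadline | Result |
|---|---|---|---|
| Table 11, death row (IRB) | definitely related | 24 hours | not triggered |
| Table 10 footnote (OnCore) | unexpected and definitely related | 24 hours | not triggered |
| Section 9.6.1 (OnCore) | DLT | 5 calendar days | applies if a DLT under 9.9 |
| Table 10, highest-grade cell (OnCore) | related event | 7 days (apparent reading; the table is broken in the text) | applies |
| Table 11, serious-event row (IRB) | serious and unexpected | 7 calendar days | only if unexpected |
| Section 9.6.3 (FDA) | unexpected fatal suspected reaction | 7 calendar days | only if unexpected |

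The IRB deadline moves from 1 day to 7, a difference of 6 days. At the projected 16 participants a year (Section 8.3), 16 × 6 / 365 = 0.26 participants would be expected to enter in that interval.

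**Step 3. Is a fatal event with a listed term unexpected?** Take fatal colitis.
- By Section 9.1.2: colitis is listed in Tables 5 and 6, so it is expected. The 7-day IRB and FDA routes do not apply, and Section 9.6.3 leaves it to the IND annual report.
- By the grade-based wording of Section 1.6: Table 5 shows 1 grade 4 colitis in 511 patients, 1/511 = 0.2%, below 4%. Table 5 has no grade 5 column, and Table 6 marks colitis only to grade 3. Fatal colitis is then unexpected and both 7-day routes apply.

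The two definitions give opposite answers.

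**Step 4. How often might this arise?** The documents give no fatal rate for this combination, so the rates here are assumptions. P(at least one in 27) = 1 − (1 − p)^27:
- p = 1%: 23.8%
- p = 2%: 42.0%
- p = 5%: 75.0%

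**Step 5. Does a death pause accrual by itself?** First, the plan's own figures from Section 8.5, with p0 = 0.15, p1 = 0.30 and both errors 0.10:
- D = ln[0.30 × 0.85 / (0.15 × 0.70)] = 0.8873
- slope = ln(0.85/0.70) / D = 0.2188 (plan: 0.219)
- upper intercept = ln(0.90/0.10) / D = 2.4763 (plan: 2.476)

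Rounding intercept + slope × n up to a whole number reproduces Table 8 at every n from 4 to 27 except n = 16, where the line is 5.977 (bound 6) and the table gives 7. That is a separate minor point. The lowest tabulated bound is 4 DLTs, and extending the line to n = 1, 2, 3 gives 3, 3 and 4. One death, counted as one DLT, cannot reach the bound at any n.

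**The case against.** A reader might infer that the 24-hour route can never be triggered by any treatment-related death. The documents do not support that. Four ipilimumab doses and six vaccines are planned, so an event that eased after one dose and recurred fatally after a later one could qualify as 'definite'. Table 11 speaks of study participation, which is wider than the drug-based wording of Section 9.2.1, and could cover a death from a study biopsy. The note disclaims any need for re-exposure, and the criterion it qualifies is damaged in the text. These points limit the finding to drug-related deaths from first-occurrence events. They do not remove it, because the recurrence condition itself is intact.

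A reader might also infer that such a death would go unreported. It would not. OnCore entry remains, as do the 7-day IRB and FDA routes if the event is unexpected. Section 9.12 has the DSMC review all adverse events and raise issues of immediate concern. On the grade-based reading a fatal event is unexpected, so the missing IRB row in Step 3 is an ambiguity and not an established gap.

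Finally, a reader might take the absence of an automatic accrual pause for a single death as an error. It is a design choice. Table 8 is a non-binding rate guideline, and the DSMC and study team keep discretion to act. A pause keyed to 'possible' would have a real cost: Section 9.2.1 defines that class as a link thought improbable though not excludable, and cohort 1 has advanced disease with a high background risk of death.

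**Conclusion.** The point holds in a limited form. Followed as written, Section 9.2.1 keeps a drug-related death from a first-occurrence event out of the 'definite' class, and so out of both 24-hour routes. Its note also pulls against itself by demanding an observed recurrence while not requiring re-exposure.

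The size is six days on the IRB deadline if the event counts as unexpected. If its term is listed and Section 9.1.2 is read literally, no prompt IRB adverse-event row applies. This assumes that staff apply the Section 9.2.1 definition when using Tables 10 and 11. Table 11 does not cite it, but it is the only definition of 'definite' in the document. The finding is about reporting speed and internal consistency. It does not show that safety oversight is absent, and the lack of an automatic pause for a single death is not part of it.

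**What to change.** 1. Reconcile Section 9.2.1 with Tables 10 and 11 in one of two ways. Either exempt fatal or irreversible events from the resolution and recurrence criteria for 'definite', as 'probable' already does for non-resolving events, or key the 24-hour triggers for deaths to 'probably or definitely related'. If Table 11 reproduces IRB policy, the first option remains within the sponsor's control.
2. Reword the 'definite' note so that its statements on re-exposure and recurrence agree.
3. State in Section 9.1.2 that expectedness is judged by grade, in line with Sections 1.5 and 1.6.

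The cost is a wording amendment and a few more 24-hour reports. No sample-size or analysis change follows.

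Optional, for the sponsor and DSMC to weigh: whether a treatment-related death should suspend accrual pending review, using the review path already written for a crossed bound. The attribution level that triggers it would need thought, for the reason given above about 'possible'.
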